The Bridge device, currently FDA approved for opioid use disorder, acts as a peripheral nerve stimulator/modulator. Nerves potentially affected by the electrodes placed on and around the ear include the auriculotemporal branch of the Mandibular Nerve, the posterior auricular branch of the Facial Nerve, the Glossopharyngeal Nerve, and the auricular branch of the Vagus Nerve, as well as the peripheral occipital and greater auricular nerves. This stimulation is believed to provide analgesic effects through influence on various neurotransmitters, including serotonin, norepinephrine and GABA, and has resulted in 56-75% reduction of opioid requirements in major abdominal surgery (4).

The device has an integrated 3 volt battery, with an impedance range of 1 to 10 kilo-ohms. It provides symmetrical, biphasic stimulation at a frequency of 0.125 Hz. Its package notes that it is contraindicated for patients with pacemakers, those with hemophilia (since the electrodes involve a micro-needle puncture), and psoriasis involving the ear. We would broaden this to include any patient with active anticoagulation, or any dermatologic condition involving the skin of the ear where the device would be placed.

Study Hypothesis: Use of the Bridge device will reduce opioid requirements (after resolution of block) by more than 33% on postoperative days 1 through 5.

Primary Outcome: Cumulative Oral Opioid Use (expressed as Oral Morphine Equivalents) on Postoperative days 1 through 5.

Secondary Outcomes: NRS pain scores recorded every four hours on postoperative days 0 to 4,
Oral opioid use on Individual Postoperative days 5 through 7
NRS pain scores recorded every 8 hours on postoperative days 4 to 7
Adverse effects related to opioids (nausea, dizziness, vomiting, itching)
Local adverse effects on ear related to use of bridge device (pain, etc)

Setting: UPMC West Mifflin Ambulatory Surgery Center, West Mifflin, PA. Specifically with use in ambulatory rotator cuff repair patients.

Subjects: We plan to enroll 15 patients in this observational, "proof of concept" study, in order to evaluate whether a 33% reduction in opioid use is possible over postoperative days 1 through five (after resolution of block), as compared to historical controls.

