Procedures: Informed consent will be obtained, per IRB requirements. Standard anesthesia will be provided for rotator cuff repair for all patients. This includes single-shot bupivacaine interscalene nerve block with propofol sedation for the surgery itself, followed by application of the Bridge device in consented patients. Application of Bridge device occurs after surgery in recovery area. The ear is scrubbed with alcohol and electrodes placed in the required areas on or just in front of auricle. The device is then activated in the PACU. Patients will fill out a "pain diary" at home to record oral opioid use and pain scores as noted above, for first seven days after surgery. A study coordinator will call the patients on postoperative day 1, 3 and 7 to evaluate them. The device becomes inactive after 5 days and will be removed and discarded. At the end of 7 days, patients will fill out a Quality of Recovery survey, as well as a survey about the impact of the use of the device on their pain and recovery.

Endpoints: These include the primary and secondary outcomes noted above. At the end of five days, the device will be removed by the patient and discarded. Any patient who develops pain or skin irritation (or other adverse reaction) from the Bridge device will be advised to remove it and their participation will be stopped at that time.

Data Analysis: Descriptive statistics will be utilized, including comparison to historic controls. Mean pain values based on recorded NRS score for each postoperative day will be compared between groups. For the primary outcome, opioid ingestion over the entire interval of postoperative days 1 to 5 will be expressed as mean OME for each group, reported with 95% confidence interval. In pain scores, a difference of at least 1.7 on NRS scoring is considered to represent a meaningful clinical difference for shoulder surgery.

1. Abdallah FW Anesth Analg 2015;120:1114.
2. Hussain N. Anesthesiology 2021;134:147
3. [name]. J Complement Integr Med 2021 doi:10.1515/jcim-2021-0208

4. Ilfeld BM Reg Anesth Pain Med 2022;47:581

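### A reaction to the device ends participation, not only device wear, so the POD 1-5 opioid total is incomplete for patients stopped early, and the plan does not say how they are analysed

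*Combined protocol and SAP*

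**What the plan says.** The Endpoints section says that a patient with ear pain, irritated skin or any other reaction to the device "will be advised to remove it and their participation will be stopped at that time". No severity threshold is given. The device is switched on in the recovery area on the day of surgery, so a stop can come at any time from POD 0 onward.

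The outcomes that depend on continued participation are:

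- **Primary Outcome:** "Cumulative Oral Opioid Use (expressed as Oral Morphine Equivalents) on Postoperative days 1 through 5". Data Analysis adds that "opioid ingestion over the entire interval of postoperative days 1 to 5 will be expressed as mean OME for each group", with a 95% confidence interval (CI).
- **Secondary Outcomes:** "Oral opioid use on Individual Postoperative days 5 through 7", "NRS pain scores recorded every 8 hours on postoperative days 4 to 7", and local ear effects of the device.

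Under Procedures, the data come from a diary kept "at home to record oral opioid use and pain scores as noted above, for first seven days after surgery", from phone contact ("A study coordinator will call the patients on postoperative day 1, 3 and 7 to evaluate them"), and from surveys at day 7. The same section says of the device: "The device becomes inactive after 5 days and will be removed and discarded".

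Data Analysis defines no analysis set and gives no rule for missing or partial opioid totals. Nothing says whether a stopped patient is replaced.

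**The concern.** The Endpoints sentence joins two separate actions. Taking the device off ends exposure; stopping participation ends data collection. Only the first follows from a device reaction.

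The primary outcome is a five-day sum, so a patient stopped during those days has no value for it. The plan leaves two ways to proceed:

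- **Exclude the patient.** The mean then describes only patients who tolerate the device. The direction of bias is unknown. It favours the device if stopped patients would have used more opioid than completers, works against it if less, and vanishes if equal. The CI also widens.
- **Count the partial sum as a total.** This lowers the device mean whatever the device does. It fits poorly with an outcome defined over the whole interval.

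The rule can act only on the device group; how complete the historical-control data are is not described. The ear reaction that triggers the stop can be recorded, but follow-up of ear effects then ends in the patients who have them. The later opioid and pain outcomes are lost as well.

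**Working it through.** **Inputs from the documents.** Planned enrolment is 15, the outcome window is POD 1-5, and the reduction of interest is 33%. The figure of 15 cannot be reproduced, because no alpha, power, SD, control mean or dropout rate is given. Nothing below depends on it being right.

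**Assumptions (the documents give none of these).** Stop rate p; number stopped k; stopped patients' use relative to the completers' mean, R; share of five-day use recorded before the stop, s; coefficient of variation (CV) of the opioid total.

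**1. How likely are stops?** Binomial with n = 15:

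| p | at least one stop | three or more |
|---|---|---|
| 2% | 26% | 0.3% |
| 5% | 54% | 3.6% |
| 10% | 79% | 18% |

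**2. Exclusion, no true device effect.** The true mean is [(15 - k) + kR]/15 times the completers' mean, so the apparent reduction is 1 - 15/[(15 - k) + kR].

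| R | k = 1 | k = 3 |
|---|---|---|
| 0.5 | 1 - 15/14.5 = -3.4% | 1 - 15/13.5 = -11.1% |
| 1 | 0% | 0% |
| 1.5 | 1 - 15/15.5 = 3.2% | 1 - 15/16.5 = 9.1% |
| 2 | 1 - 15/16 = 6.2% | 1 - 15/18 = 16.7% |

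**3. Exclusion, precision.** The 95% CI half-width in SD units is t(0.975, n - 1)/sqrt(n). Multiplying by an assumed CV of 0.5 to 1.0 gives it as a share of the mean.

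| n | half-width (SD) | change | share of mean |
|---|---|---|---|
| 15 | 0.554 | - | 28-55% |
| 14 | 0.577 | 4% wider | 29-58% |
| 12 | 0.635 | 15% wider | 32-64% |

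**4. Partial sums counted as totals.** The fall in the device mean is k(1 - s)/15. With equal daily use, s = 0.20, 0.40 or 0.60 after POD 1, 2 or 3. With falling use (30/25/20/15/10% over the five days), s = 0.30, 0.55 or 0.75.

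- One stop: 0.25/15 = 1.7% to 0.80/15 = 5.3%.
- Three stops: 5% to 16%.
- Stops before POD 1 (s = 0): 1/15 = 6.7% for one and 3/15 = 20% for three.
- Reaching 33% with no device effect would take five stops before POD 1 (5/15). At p = 10%, five or more stops at any time have a probability of about 1.3%.

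**5. Is the data loss required by the design?** The device is inactive after day 5, while the diary runs to day 7. The plan therefore already collects data from patients with no active device, and the same diary and calls would serve a patient who removed it sooner.

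**The case against.** The best counter-argument has five parts.

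- **Participation is undefined.** No sentence says in words that the diary or calls end, and the consent form, which is not in the text reviewed, may address data after withdrawal. This limits certainty about follow-up. But device removal is stated separately in the same sentence, so stopping participation must mean something more, and nothing says collection continues. If the narrower meaning was intended, one sentence would settle it.
- **Pain scores are partly covered.** Data Analysis uses recorded scores for each day, so scores from before a stop can be used. This stands, but it does not help the cumulative opioid total.
- **Exclusion is not stated.** The wording about the whole interval may only contrast one five-day total with daily means. This is a fair caution, and it is why both readings are quantified above.
- **Describing patients who wore the device is a legitimate aim for a 15-patient proof of concept.** It is, and a while-wearing summary serves it. The reader still needs to know whom the primary mean covers.
- **The magnitudes are all assumed.** They are, and the Background describes the device as causing no symptoms and being easily tolerated, which points to few stops. Even three excluded patients with R = 2 give 16.7%, about half the 33% of interest. This supports a minor rating; it does not remove the gap.

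**Conclusion.** The concern holds, as a minor point. Followed as written, the rule loses the POD 1-5 opioid total in the patients who react to the device, and the plan does not say how they enter the mean. Confidence is high for the text and low for the size, because stop rate, relative opioid use, timing and variability are all assumptions.

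One stop among 15 shifts the result by a few percent, small beside a CI half-width of roughly 28-55% of the mean at the assumed CV. Several stops would matter more. The study is descriptive and has no pass/fail test, so this does not decide its result. Data not collected at the time may not be recoverable later.

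**What to change.** Leave the device-removal advice unchanged. In Endpoints, replace the clause that ends participation with: *the patient continues the diary, the remaining scheduled calls and the day 7 surveys, unless the patient withdraws consent.*

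Add a short paragraph to Data Analysis:

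- Analyse the primary outcome in all patients in whom the device was applied, and do not treat partial sums as complete totals.
- Report the number and timing of removals, with a while-wearing summary alongside.
- For patients who withdraw consent, report the complete-case mean and CI, with a sensitivity range for the missing days, for example 0.5 to 2 times the completers' daily use. With equal daily use and withdrawal after POD 1, each such total lies between 0.2 + 0.8 × 0.5 = 0.6 and 0.2 + 0.8 × 2 = 1.8 of a completer's. The mean then moves by -2.7% to +5.3% for one patient and -8% to +16% for three.
- Do not compute the CI from totals filled in at the completers' mean. With 3 of 15 filled in, the half-width would be 0.554 × sqrt(11/14) = 0.491 SD against 0.635 SD at n = 12, which is 23% too narrow.

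Ask about the ear at the remaining calls, and record the time of removal.

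**Cost.** One changed sentence, one paragraph and two items added to the existing diary and calls. A protocol amendment through the IRB and revised consent wording are likely. Patients who remove the device would keep the diary to day 7, and the estimate may be less favourable to the device.

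### The study asks whether opioid use falls by more than 33% against historical controls, but no interval is planned for that reduction and the controls are not stated to be fixed in advance

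*Combined protocol and SAP*

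**What the plan says.** The Study Hypothesis is quantitative: "Use of the Bridge device will reduce opioid requirements (after resolution of block) by more than 33% on postoperative days 1 through 5". The Primary Outcome matches it: "Cumulative Oral Opioid Use (expressed as Oral Morphine Equivalents) on Postoperative days 1 through 5". The Subjects paragraph plans 15 device patients in an observational proof-of-concept study; the question it sets is "whether a 33% reduction in opioid use is possible over postoperative days 1 through five (after resolution of block), as compared to historical controls".

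Data Analysis answers with "Descriptive statistics will be utilized, including comparison to historic controls". For the primary outcome, opioid intake over the interval "will be expressed as mean OME for each group, reported with 95% confidence interval". It names no difference, ratio or percentage reduction, and no interval for one.

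Under Procedures, device patients fill in a diary "at home to record oral opioid use and pain scores as noted above", and a coordinator calls them on days 1, 3 and 7. The anesthetic is described for all patients: "This includes single-shot bupivacaine interscalene nerve block with propofol sedation for the surgery itself". For the historical controls, the documents give no source, dates, number, eligibility, or method of recording intake, and do not say when the set is chosen.

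**The concern.** The percentage reduction against controls is the study's one quantitative question, and it depends on two things that the plan leaves open.

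The first is the denominator. The control mean enters the percentage directly. If the calendar window or source can be settled after device results are known, or if control intake was captured in some way other than a prospective home diary, the reduction partly reflects that choice. No sampling interval covers this.

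The second is precision. The plan commits to 95% intervals but attaches them to the two group means, not to the reduction. A report could follow the plan to the letter, state a reduction near 33%, and never set the uncertainty of that figure against the 33% threshold.

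**Working it through.** **Plan's own figure.** The only design number is 15 device patients. It comes with no variance, control mean, error rate or power, so there is no calculation to reproduce.

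**Inputs.** From the documents: 15 device patients; a threshold of 33%, so an observed ratio of means of 0.67 sits exactly on it. Assumed, because the documents give neither: coefficient of variation (CV, standard deviation divided by mean) of 0.6, 0.8 or 1.0, equal in both groups; number of controls m of 15, 50 or 100.

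**Step 1: interval for the reduction.** Log ratio of means, delta method:

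- SE = CV × √(1/15 + 1/m)
- 95% limits for the reduction = 1 − 0.67 × exp(±t × SE), with t on Welch degrees of freedom (28.0, 23.1 and 18.5 for m = 15, 50 and 100; t = 2.048, 2.068 and 2.097)

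Narrowest case, CV 0.6 and m = 100: SE = 0.6 × √(0.0667 + 0.0100) = 0.166; t × SE = 0.348; limits 1 − 0.67 × e^0.348 = 5.1% and 1 − 0.67 × e^−0.348 = 52.7%.

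Widest case, CV 1.0 and m = 15: SE = 1.0 × √(0.0667 + 0.0667) = 0.365; t × SE = 0.748; limits −41.6% and 68.3%.

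| Controls | CV 0.6 | CV 0.8 | CV 1.0 |
|---|---|---|---|
| 15 | −4.9% to 57.2% | −21.9% to 63.2% | −41.6% to 68.3% |
| 50 | 3.5% to 53.5% | −9.1% to 58.8% | −23.2% to 63.6% |
| 100 | 5.1% to 52.7% | −6.6% to 57.9% | −19.7% to 62.5% |

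In simulation (40,000 gamma-distributed runs per setting, true ratio 0.67, no drift), this interval covered the truth 93.4% to 94.6% of the time across the nine settings. It is therefore usable at this sample size.

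**Step 2: what the planned summaries would show.** Scale the control mean to 100 and the device mean to 67. At CV 0.6 with 50 controls, the separate t intervals are 67 ± 2.145 × 40.2/√15 = 44.7 to 89.3 (device) and 100 ± 2.010 × 60/√50 = 82.9 to 117.1 (controls). Neither is an interval for the reduction. A reader who has both group sizes can recover the standard errors, 22.3/2.145 = 10.40 and 17.1/2.010 = 8.51. The log-ratio SE is then √((10.40/67)² + (8.51/100)²) = 0.177, and the reduction interval is about 3.4% to 53.5%, against 3.5% to 53.5% computed directly.

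**Step 3: error in the historical mean.** Let d be the historical mean divided by the mean that untreated patients would have today (assumed).

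- True reduction that reads as 33% = 1 − 0.67 × d: 26.3% at d = 1.1; 19.6% at d = 1.2.
- A true 33% reads as 1 − 0.67/d: 25.6% at d = 0.9; 16.2% at d = 0.8.
- No effect reads as 33% only when d = 1/0.67 = 1.49.

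**The case against.** The strongest reply is that this is a 15-patient descriptive study asking whether a 33% reduction is possible. It has no test, error rate or decision rule, so a missing contrast interval is close to a matter of taste. The first part stands: the absence of a formal test is not a defect here. But an interval for an estimate is itself descriptive, and the plan already promises intervals, only for other quantities.

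A reader might infer that the planned group intervals say nothing about the precision of the reduction. The documents do not support that. Step 2 shows that the interval can be approximated if group sizes are reported and t intervals are used, and a device interval of 45 to 89 around 67 already signals wide uncertainty. What is missing is the reported contrast and its comparison with 33%. Nor do the group intervals generally mislead by overlapping: they overlap while the reduction's interval excludes zero in only 2 of the 9 settings (CV 0.6 with 50 or 100 controls), and that contrast concerns zero, not 33%.

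A reader might also infer that controls will be picked after the device results, or that adjustment is ruled out. The documents say neither. They are silent on both, and the control set may be defined in a document not supplied.

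Finally, every magnitude above is assumed, and reporting an interval displays imprecision without reducing it. Both are true. The control-selection gap does not depend on those figures.

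**Conclusion.** The point holds in a limited form. The plan poses a quantitative question against historical controls, does not state that those controls are fixed in advance or comparably recorded, and does not report an interval for the reduction or set one against 33%. Under the assumed CVs and control numbers, an observed 33% is compatible with anything from about 5% to 53% at best to −42% to 68% at worst. An assumed 10% to 20% error in the historical mean is enough to move a result across the study's threshold.

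A reader might infer that control drift alone could manufacture the hypothesized result. Step 3 does not support that for modest drift: with no device effect, the historical mean would have to be about 49% too high. Drift of 10% to 20% matters when the true effect is near 33%.

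This should be changed, but it does not invalidate the study. Confidence is medium, because the documents give no spread, control number or drift.

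**What to change.** Before any device outcome is read:

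- Lock a list of controls: rotator cuff repairs at the same center, with the same single-shot block and sedation, from a stated recent calendar window.
- Require that intake on postoperative days 1 to 5 was actually recorded for each control, and state how.

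In the analysis:

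- Beside the two group means, report the percentage reduction (1 minus the ratio of means) with a 95% interval, and set it against 33%.
- State that this interval does not cover bias from era or from recording method.
- If comparable control intake does not exist, describe the device group alone and make no claim that 33% was reached.

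The cost is analysis wording and a record review, with no more device patients. Stricter selection may leave fewer controls and a wider interval: at CV 0.8, going from 100 controls to 15 changes it from −6.6% to 57.9% into −21.9% to 63.2%. The larger potential cost is that the 33% claim, which is the study's stated aim, may have to be given up.

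### The hypothesis is a reduction of more than 33% in day 1–5 opioid use, but the plan commits to no interval for that reduction and no rule for reading it against 33%

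*Combined protocol and SAP*

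**What the plan says.** The Study Hypothesis reads: "Use of the Bridge device will reduce opioid requirements (after resolution of block) by more than 33% on postoperative days 1 through 5". The primary outcome is "Cumulative Oral Opioid Use (expressed as Oral Morphine Equivalents) on Postoperative days 1 through 5". The Subjects paragraph gives the purpose of the 15 patients in softer terms, "in order to evaluate whether a 33% reduction in opioid use is possible over postoperative days 1 through five", and names historical controls as the comparator. It calls the study an observational proof of concept.

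The Data Analysis section opens with "Descriptive statistics will be utilized, including comparison to historic controls". For the primary outcome it adds that opioid ingestion over days 1 to 5 "will be expressed as mean OME for each group, reported with 95% confidence interval". It names no ratio, difference or percent reduction for opioid use. The only benchmark in that section is 1.7 points on the NRS, which applies to pain scores. The source, number, mean and SD of the historical controls are not given.

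**The concern.** The hypothesis concerns a relative quantity with a threshold, while the planned output is two separate means. The group means do have planned uncertainty. What is missing is an interval for the reduction and a statement of what result would count as support for more than 33%.

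Without these, a point estimate just beyond 33% could be reported as showing the hypothesis when the data are equally compatible with a much smaller reduction. Two group intervals read side by side do not settle the matter when the control mean has sampling error of its own, because their overlap is not a test of the ratio. At stake is how the main result is estimated and worded. The estimate is not biased by this gap, no data are lost and no procedure changes.

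**Working it through.** **Inputs from the documents.** Bridge group n = 15; threshold 33% (ratio of means 0.67); confidence level 95%; and, from the device description, a 56–75% opioid reduction reported in major abdominal surgery, the only percentage effect quoted. No derivation is given for the 15, so there is no planning figure to reproduce.

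**Assumed inputs.** CV of five-day opioid use 0.5 to 1.2, the same in both groups; number of controls n_c = 15, 30 or 50; gamma-distributed data in the simulations; controls comparable with the Bridge patients.

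**Interval for the reduction.** Let R = Bridge mean / control mean.

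- SE(log R) = √(CV²/15 + CV²/n_c), with Welch degrees of freedom.
- CI for the reduction = 1 − R·exp(± t·SE).
- Example, CV 0.5 and n_c = 30: SE = √(0.25/15 + 0.25/30) = 0.158, df = 28.1, t = 2.048. With R = 0.67 the ratio limits are 0.67·exp(∓0.324) = 0.485 and 0.926, a reduction of 7.4% to 51.5%.

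Reduction CIs with 30 controls (negative = increase):

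| CV | Observed 33% | Observed 56% | Observed 75% |
|---|---|---|---|
| 0.5 | 7% to 52% | 39% to 68% | 65% to 82% |
| 0.8 | −12.5% to 60% | 26% to 74% | 58% to 85% |
| 1.0 | −28% to 65% | 16% to 77% | 52% to 87% |
| 1.2 | −46% to 69% | 4% to 80% | 46% to 88% |

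An observed 56% excludes 33% only at CV 0.5. An observed 75% excludes it at every CV. Both statements also hold with 15 or 50 controls: for 56%, the lower limits at CV 0.5 are 36.0% and 40.3%, and at CV 0.8 they are 20.0% and 28.4%; for 75%, the smallest lower limit is 38.7% (CV 1.2, 15 controls).

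**The planned display in the same example.** Set the control mean to 100, CV 0.5, 30 controls, observed reduction 33%.

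- Bridge: 67 ± 2.145 × 33.5/√15 = 48 to 86.
- Control: 100 ± 2.045 × 50/√30 = 81 to 119.

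These overlap, yet the interval for the reduction (7% to 52%) excludes 0. It does not exclude 33%.

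**If the control mean is one fixed published figure.** The planned Bridge CI divided by it already gives an interval for the reduction. For an observed 33% it is 14% to 52% at CV 0.5 and −4% to 70% at CV 1.0.

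**How much the reading rule matters.** Simulated trials, 15 Bridge patients against 15 to 50 controls:

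| CV | True 20%: point estimate beyond 33% | True 20%: whole CI beyond 33% | True 56%: whole CI beyond 33% | True 75%: whole CI beyond 33% |
|---|---|---|---|---|
| 0.5 | 12–17% | 0.2% | 61–80% | over 99% |
| 0.8 | 24–27% | 0.7% | 30–44% | 91–98% |
| 1.0 | about 30% | about 1% | 22–32% | 76–92% |
| 1.2 | 33–35% | about 2% | 18–26% | 62–81% |

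Coverage of the log-ratio interval in these simulations was 93.0% to 94.6%, slightly under nominal.

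**The case against.** The strongest reply is that this is a descriptive proof-of-concept study. The Subjects paragraph asks only whether a 33% reduction is possible, and a point estimate with group intervals is a fair answer to that. The plan nowhere says that a point estimate beyond 33% will be declared a success, so the 12–35% rates describe a rule it has not adopted. The overlap example also errs towards caution rather than over-claiming, and it arises at the low end of the assumed CVs: at 0.8 and above with 30 controls, the interval for an observed 33% reduction includes 0 as well. If both group sizes are reported, a reader can rebuild the interval, and it can be added at analysis without new data.

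Much of this stands. No formal test is needed. With a fixed control mean the gain is only in presentation and stated reading. The undefined control source is a prior problem that must be solved first. What does not stand is that the descriptive label excuses the omission. The plan already commits to 95% intervals, but not to one for the quantity it hypothesises. It does not promise the control number a reader would need. Its two wordings of the aim leave the criterion open, so the reading could be chosen after the result is known.

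**Conclusion.** The concern holds and should be fixed. The stated analysis does not estimate the hypothesised percent reduction with its uncertainty, and nothing fixes how the result will be read against 33%. That much follows from the text alone.

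The practical size rests on the assumed CVs and control numbers and is illustrative. Within those ranges, the choice between reading the point estimate and reading the interval largely decides whether a modest true effect could be reported as meeting the hypothesis. The 56–75% benchmark comes from a different type of surgery. No sampling interval covers bias from using historical controls.

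**What to change.** In Data Analysis, define the primary estimate as the percent reduction, 100 × (1 − mean Bridge OME / mean control OME) over days 1 to 5, with a 95% CI. A Welch-type interval on the log ratio of means, using the control mean, SD and n, would serve; it allows individual zeros but not a group mean of zero. If only a control mean exists, treat it as fixed and say that its uncertainty is ignored. Keep the group means and their intervals as descriptive output.

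Add one sentence on reading: the estimate and its CI will be read against both 0 and 33%; a point estimate beyond 33% will not by itself be reported as showing a reduction of more than 33% when the CI includes 33%; and the CI does not cover bias from historical controls.

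The cost is two or three sentences, plus naming the control source and the summary available from it. The downside is a wide interval and often a less favourable conclusion: as the last table shows, even a true 56% reduction would often leave 33% inside the CI. A very large effect would usually still show.
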